**NCT 02837328**

**July 5th, 2018**

## **Materials and Methods**

The study was registered at Clinicaltrials.gov (# NCT02837328). The study protocol was approved by the University of Minnesota Institutional Review Board, and all participants provided written informed consent.

### *Study participants*

Participants 55 years of age or older were recruited using fliers, the University of Minnesota StudyFinder website, invitations to individuals enrolled in the ResearchMatch research volunteer database, and invitations to University of Minnesota School of Public Health employees.

Exclusion criteria included a prior history of heart disease (coronary heart disease, heart failure, AF), stroke, known kidney disease; use of type I or III antiarrhythmic drugs or digoxin; current use of magnesium supplements; any prior history of allergy or intolerance to magnesium; lactose intolerance; prior history of inflammatory bowel disease or any severe gastrointestinal disorder. Use of multivitamins was allowable, since these typically contain relatively low dosages of Mg (e.g. 50 mg).

Eligible participants attended a baseline visit where measurements were conducted and a Zio® XT Patch (ZioPatch; iRhythm Technologies, Inc., San Francisco, California) heart rhythm monitor was applied by trained staff. After wearing the ZioPatch for 2 weeks, participants were randomized 1:1 to either 400 mg magnesium oxide or placebo using block randomization within two strata of age (younger than 65 and 65 and older). The randomization was carried out separately for the two randomization strata, age younger than 65 and 65 and older. In each group, a randomization schedule was generated using randomly permuted blocks of random sizes.

Block sizes of 2, 4 or 6 were permitted. The randomization was implemented using the `blockrand` package in R.

Following randomization, participants were mailed the study intervention, which they took for a total of 12 weeks. Ten weeks after beginning the study intervention, participants took part in a follow-up clinic visit, and a second ZioPatch was applied. Participants continued the study intervention until the second ZioPatch was removed (2 weeks after the follow-up clinic visit) (Figure 1).

### *Study intervention and blinding*

The University of Minnesota Institute for Therapeutics Discovery and Drug Development produced the active study intervention (400 mg magnesium oxide) and matched placebo (lactose) according to Good Manufacturing Practices. The University of Minnesota Investigational Drug Service managed bottling per the randomization scheme. Study participants and all study staff were blinded to the treatment given.

### *Measurements*

At the baseline and follow-up clinic visits, participants completed questionnaires and trained study staff conducted physiological measurements (i.e., anthropometry, blood pressure), phlebotomy, and applied the ZioPatch device. Treatment compliance was assessed by a pill count at the follow-up visit. At intervention days 21, 42 and 80 participants were also emailed unique links to online questionnaires, administered via REDCap [15], which queried compliance and asked the following open-ended question about adverse effects: “Since starting the study,

have you experienced anything out of the ordinary?” Participant blinding was also assessed on intervention day 80, the last day of the study.

The ZioPatch was used to identify premature atrial contractions (PACs). PACs are supraventricular arrhythmias associated with the future risk of AF [16-18] and are considered an intermediate phenotype of the arrhythmia, reflecting the underlying cardiac substrate that facilitates the development of AF [19]. Participants were asked to wear the ZioPatches for 2 weeks after each clinic visit. Information obtained from the ZioPatch devices was processed by the ZEUS algorithm, a comprehensive system that analyzes electrocardiographic data received from the device [20]. We counted as PACs isolated supraventricular ectopic beats, supraventricular ectopic couplet total count, and supraventricular ectopic triplet total count. Total PACs were then divided by number of hours the ZioPatch recorded analyzable data, which yielded PACS per hour.

Participants were asked to fast for 8 hours prior to blood draws. Serum magnesium and glucose were measured using the Roche Cobas 6000 at the University of Minnesota Advanced Research and Diagnostic Laboratory. Blood pressure was measured with the participant sitting, after a 5 minute rest, with a random zero sphygmomanometer (Omron Digital Blood Pressure Monitor HEM-907XL). Three measurements were taken; all three measurements were averaged for use in analyses. Height and weight were measured with participants in light clothing, and shoes removed. Height was measured with a research stadiometer and weight with a scale.

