**NCT 02837328**

**July 5th, 2018**

### *Statistical analysis*

The goal of the pilot study was to assess adherence to the Mg supplement, and feasibility of using the ZioPatch and collect preliminary data on PACs, a predictor of AF. The targeted sample size of 60 was determined to detect a difference in the change in log PACs (follow-up minus baseline) between treatment groups of 0.79 standard deviation units with 80% power and 5% type I error (2-sided), assuming 5 participants would not complete follow-up.

All analyses were intent-to-treat. Descriptive statistics are provided according to treatment assignment for baseline characteristics, adherence, Mg concentrations and other outcomes. Differences in baseline characteristics between groups were assessed using t-tests for continuous variables and Fisher's exact tests for categorical variables. Linear regression was used to evaluate whether change in outcomes differed according to treatment assignment, adjusting for the randomization stratification factor (age  $\geq 65$  vs  $< 65$ ) and baseline value of the outcome with robust variance estimates for confidence intervals and P-values. Post-hoc sensitivity analyses further adjusted for sex. As PAC burden is highly skewed, we pre-specified using log PAC burden for analysis and reported the ratio of geometric means. Pre-specified subgroup analyses were also performed, stratified by baseline magnesium concentration ( $<$  vs.  $\geq$  median). A 2-sided p-value of  $< 0.05$  was used to indicate statistical significance. Analyses were conducted using R [21] version 3.4.0 (R Foundation, Vienna, Austria).

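### The one adverse-effect question described counts from the start of the study, so on-treatment rates per arm cannot be cleanly separated from events in the two untreated baseline weeks, or new events from repeats

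*Protocol*

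**What the plan says.** The Protocol, under Measurements, states that "At intervention days 21, 42 and 80 participants were also emailed unique links to online questionnaires". These asked about compliance and "asked the following open-ended question about adverse effects": "Since starting the study", "have you experienced anything out of the ordinary"? The same question is described for all three surveys. No onset date, severity, baseline symptom question or rule for repeated reports is described.

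Under Study participants, the order of events is a baseline visit, a period of monitor wear, randomisation and then treatment: "After wearing the ZioPatch for 2 weeks, participants were randomized 1:1", and "Following randomization, participants were mailed the study intervention". The transit time is not given.

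The SAP (Statistical analysis) promises descriptive statistics by assigned arm for baseline characteristics, adherence, "Mg concentrations and other outcomes". It does not mention adverse effects by name and gives no counting rule for them.

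**The concern.** A participant starts the study, in the ordinary sense, at the baseline visit. The pills arrive at least two weeks later. An event in those two weeks is a truthful answer to the question as worded, although no treatment had been taken. All three surveys share the same starting point, so an event at day 10 of treatment can properly be reported at days 21, 42 and 80.

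What is at stake is the tolerability figure from each arm. Tolerability is not one of the pilot's stated goals, but adherence is the first of them and adverse effects are a plausible reason for stopping pills. A later trial would probably look to this pilot for the proportion on magnesium who report a problem. That per-arm proportion is what the wording blurs most. The comparison between arms is much less exposed.

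**Working it through.** The documents give no figure for adverse effects, so there is nothing of the plan's own to reproduce. The check is day arithmetic, followed by two illustrations with assumed rates.

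**Inputs from the Protocol.** Untreated baseline: 2 weeks = 14 days (Study participants). Survey days: 21, 42 and 80 of the intervention (Measurements). **Assumed:** a gap of 0 to 7 days between randomisation and first pill, since the mailing time is not stated.

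**Step 1. Untreated share of the literal window** = (14 + lag) / (14 + lag + survey day).

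| Survey | No lag | 7-day lag |
|---|---|---|
| Day 21 | 14/35 = 40% | 21/42 = 50% |
| Day 42 | 14/56 = 25% | 21/63 = 33% |
| Day 80 | 14/94 = 15% | 21/101 = 21% |

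**Step 2. Overlap (no lag).** The windows total 35 + 56 + 94 = 185 days but cover only 94 distinct days. A baseline event can be reported three times. An on-treatment event can be reported (21×3 + 21×2 + 38×1)/80 = 143/80 = 1.79 times on average at a constant rate. If raw mentions were summed, 14×3/185 = 42/185 = 23% of them could be pre-treatment.

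**Step 3. Effect on the comparison at day 21.** Assume a background rate of 5% per week in both arms and a further 5% per week on magnesium while treated. The probability of at least one event is 1 − exp(−cumulative rate).

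- Treated weeks only: placebo 1 − exp(−0.15) = 13.9%; magnesium 1 − exp(−0.30) = 25.9%. Difference 12.0 points, ratio 1.86.
- With the two baseline weeks added: placebo 1 − exp(−0.25) = 22.1%; magnesium 1 − exp(−0.40) = 33.0%. Difference 10.8 points, ratio 1.49.

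In this model the difference is multiplied by the probability of no baseline event, here exp(−0.10) = 0.905, and 12.0 × 0.905 gives the 10.8 (10.9 if the rounded percentages are subtracted).

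**Step 4. Range of rates, ever reported by day 80.** Assume a constant rate, an on-treatment placebo risk p, and a hazard ratio of 2 on magnesium. The baseline weeks multiply each event-free probability by (1 − p)^(14/80). The placebo figure becomes 1 − (1 − p)^(94/80), and the magnesium figure goes from 1 − (1 − p)² to 1 − (1 − p)^(2 + 14/80).

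| Placebo on treatment | Placebo as worded | Difference (points), on treatment → as worded | Ratio, on treatment → as worded |
|---|---|---|---|
| 5% | 5.8% | 4.75 → 4.71 | 1.95 → 1.80 |
| 10% | 11.6% | 9.00 → 8.84 | 1.90 → 1.76 |
| 20% | 23.1% | 16.00 → 15.39 | 1.80 → 1.67 |
| 40% | 45.1% | 24.00 → 21.95 | 1.60 → 1.49 |

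**Step 5. Scale against sampling error.** With 30 per arm (60 randomised 1:1) and the day-21 treated-only rates, the 95% half-width for the difference is 1.96 × √[(0.139×0.861 + 0.259×0.741)/30] = about 20 points. The shift in Step 3 is about 1 point.

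**The case against.** A reader might infer that on-treatment tolerability is misstated. The documents do not support that, for four reasons.

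- **Reading of the question.** The surveys are timed from the start of the intervention and also ask about compliance, so some participants will take the study to mean the pills. For them the window is correct. This stands. It leaves an ambiguity, because nothing described tells the analyst which reading a participant used.
- **Balance between arms.** The extra time precedes randomisation, and participants and staff are blinded. Background events should fall equally on both arms, and the placebo arm is there to absorb them. This stands, and it is why the risk difference hardly moves. It does not protect the per-arm rate or the ratio.
- **Dating and double counting.** Answers are free text and may give a date, and the first survey to mention an event helps to bound its onset. Counting each participant as ever or never reporting removes duplication. This stands too, but the SAP states no such rule, and an ever-reported count still includes baseline events. The cumulative wording also has one merit: a later survey can recover events from a missed one.
- **Direction.** An open question may miss events that a prompt would elicit. Under-reporting and the longer window pull in opposite directions, so the net error is unknown.

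A reader might also infer that gastrointestinal effects were expected and that a prompted item was required. The Protocol excludes people with "prior history of inflammatory bowel disease or any severe gastrointestinal disorder" but gives no reason. The exclusion for lactose intolerance has an obvious alternative explanation, since the placebo is lactose. Open versus prompted elicitation is a debatable choice. The Protocol also summarises the questionnaires rather than reproducing them, and does not give the content of the clinic-visit questionnaires, so the point is limited to what is described.

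**Conclusion.** The concern holds in a limited form and is minor. On a literal reading, untreated time makes up 40%, 25% and 15% of the three recall windows with no mailing lag, and 50%, 33% and 21% with an assumed 7-day lag. The windows are nested, and no rule is stated for baseline events or repeats. Per-arm on-treatment rates are therefore not cleanly separable from pre-treatment events, and new events are not reliably distinguishable from repeats.

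At the assumed rates, the literal window raises the placebo figure by roughly 1 to 5 points by day 80 (8 points at day 21 in the example) and dilutes the ratio, while the difference falls by about 2 points or less. These sizes rest on constant event rates, complete recall and every participant reading the question literally. To the extent that participants read it as referring to the pills, the effect shrinks towards none. Neither the adherence measures nor the PAC analysis depends on this question.

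**What to change.** **If the surveys can still be changed.** Word the day-21 item *Since you began taking the study pills* and the day-42 and day-80 items *Since the last questionnaire*. The windows become 21, 21 and 38 days, without overlap and with no untreated time. Add to the SAP that each participant is counted once by assigned arm, as having at least one on-treatment event or none.

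**If responses are already collected**, which the past tense of both documents suggests, use the same per-participant count, set aside free-text events that describe an onset before the first pill (decided before unblinding if that is still possible), and state the recall-window limitation beside the rates. Give the risk difference prominence over the ratio, since the difference is the less affected.

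**Cost.** Two wording changes in an existing REDCap form and one sentence in the SAP; the sample size is untouched. The downside is that a participant who misses a survey has an unclear anchor at the next one, so the next survey should show the actual date from which to report.

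One related point needs reconciling: Measurements calls intervention day 80 the study's last day, whereas Study participants describes 12 weeks of treatment (12 × 7 = 84 days). If treatment runs to day 84, the last four days fall outside every survey.

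### Does naming intervention day 80 as the end of the study, when the 12-week timeline runs to about day 84, call for a change to the plan?

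*Protocol*

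**What the plan says.** The protocol's Study participants section sets out the timeline. After randomization, "participants were mailed the study intervention, which they took for a total of 12 weeks". Then: "Ten weeks after beginning the study intervention, participants took part in a follow-up clinic visit". The second ZioPatch was applied at that visit, and treatment went on until the patch came off two weeks later. The Measurements section repeats the wear time: "Participants were asked to wear the ZioPatches for 2 weeks after each clinic visit".

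The Measurements section also lists online questionnaires on intervention days 21, 42 and 80, covering compliance and adverse effects. It adds: "Participant blinding was also assessed on intervention day 80, the last day of the study". On adherence at the clinic it says: "Treatment compliance was assessed by a pill count at the follow-up visit". For the outcome it says: "Total PACs were then divided by number of hours the ZioPatch recorded analyzable data".

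The SAP's Statistical analysis section opens with the aim: "The goal of the pilot study was to assess adherence to the Mg supplement", together with the feasibility of the monitor and preliminary PAC data. It mentions neither day 80 nor any other study day.

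**The concern.** Two sections of one short protocol give different ends for the same study. A reader who takes the Study participants section at its word puts the end of treatment at day 84. One who takes the Measurements section at its word puts it at day 80.

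This looks more than cosmetic because of what is attached to day 80. The pill count is taken at the week-10 visit, so the day-80 questionnaire is the only compliance measure described for the second recording. It also carries the last adverse-effect question, and blinding is assessed only on that day. If treatment ran to day 84, all three came before treatment ended. If day 80 was the true end, the stated 12 weeks of exposure is too long, and the second recording or the visit date must differ from what is written. Since adherence is a named goal of the pilot, an unclear treatment period deserves a check.

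**Working it through.** **Inputs.** From the protocol, Study participants: 12 weeks of treatment in total; follow-up visit 10 weeks after starting; patch removal and end of treatment 2 weeks after that visit. From the protocol, Measurements: 2 weeks of wear; questionnaires on days 21, 42 and 80; day 80 named as the last day.

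**Can day 80 be reproduced?**
- From total duration: 12 × 7 = 84.
- From visit plus wear: 10 × 7 + 2 × 7 = 70 + 14 = 84.
- If the first day of treatment is day 1 and not day 0, the visit falls on day 71 and the end on day 85.
- Counting from mailing or randomization moves the end later still, because the visit is timed from the start of treatment.
- Rounding does not help: 80/7 = 11.4 weeks.

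The stated day does not reproduce. The gap is 84 − 80 = 4 days, or 5 under day-1 numbering. The documents describe no visit window or early patch removal that would explain it.

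**What each reading implies.**
1. *The questionnaire went out on the last day and only the number is wrong.* The other two questionnaire days are whole weeks (21/7 = 3, 42/7 = 6), as is 84/7 = 12, while 80 is not. This makes a misprint plausible but does not prove it, and the section gives 80 twice. On this reading nothing was missed.
2. *The questionnaire went out on day 80 and treatment ended on day 84.* The questionnaire fell 80 − 70 = 10 days into the 14-day recording. If answered when sent, it left 4 days without a described query, 4/84 = 4.8% of treatment.
3. *Treatment ended on day 80.* Exposure was 11.4 weeks. With the visit on day 70, the recording lasted 10 days. With a full 14-day recording, the visit was on day 80 − 14 = 66 (66/7 = 9.4 weeks). Intermediate cases fit too, such as a visit on day 68 with 12 days of wear.

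**Does any reading reach the analysis?** The SAP regresses the change in each outcome on treatment, adjusting for age stratum and baseline value, with PAC burden on the log scale. No study day enters the model. The sample-size statement uses a standardized difference of 0.79, 80% power, two-sided 5% error and 5 non-completers, and no treatment duration. PAC burden is a count divided by analyzable hours, so a recording of 10 days in place of 14 mainly costs some precision and leaves the scale of the outcome unchanged. One schedule is described for all participants, with participants and staff blinded, so nothing here separates the arms.

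**The case for a change.** The best case for acting is that the contradiction is plain on the page and falls on things the pilot set out to learn. A reader cannot state how long treatment lasted, how long the second recording was, or whether blinding was assessed at the end of treatment. Correcting it would cost a sentence, plus durations taken from dates the team probably holds.

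The textual conflict stands in full. Figure 1, which is not reproduced in the text available, might show which value is right, but it could not make the two sentences agree. Less of the claimed consequence stands:

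- The pill count covers 70 of 84 days (83%) because it was taken at the week-10 visit. That share would be the same if the Measurements section said day 84, so it is not an effect of this discrepancy.
- A questionnaire a few days before treatment ends is not an error. The only error is calling that day the last. Nothing in the documents requires blinding to be assessed after the final dose.
- The adverse-effect question asks about the whole time since the study began. At most, under reading 2, it misses events in the final 4 days, and late replies to the emailed link could shorten even that.
- Both documents are written in the past tense, and the SAP already names a post-hoc analysis. Moving the questionnaire date would come too late to matter.

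**Conclusion.** The concern is right that the protocol contradicts itself: about day 84 in the Study participants section against day 80 in the Measurements section, a gap of about 4 days. The passages must be reconciled, and the documents do not settle which is correct.

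It does not call for a change to the plan. The discrepancy is a clerical one in a single descriptive sentence. Its possible consequence runs from none (a misprinted day), through 4 days or 4.8% of treatment without a described query, to a treatment period of 11.4 weeks in place of 12. None of these alters the randomization, the outcome definition, the sample size or the regression model, and none implies bias between arms.

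This rests on two assumptions: that both arms followed the one schedule described, and that the PAC rate used the hours actually recorded, as the protocol says. Confidence is high that the conflict exists. Its practical effect cannot be pinned down from the documents, but it is small on every reading considered.

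### Does the PAC count go wrong by adding couplet and triplet totals to isolated beats without stating their unit, and by omitting longer runs?

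*Protocol*

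**What the plan says.** The only definition of the outcome is in the Protocol, Measurements: "We counted as PACs isolated supraventricular ectopic beats, supraventricular ectopic couplet total count, and supraventricular ectopic triplet total count". The same section turns the sum into a rate: "Total PACs were then divided by number of hours the ZioPatch recorded analyzable data, which yielded PACS per hour". It gives the source of the counts as device output: "Information obtained from the ZioPatch devices was processed by the ZEUS algorithm, a comprehensive system that analyzes electrocardiographic data received from the device", with a citation for the algorithm.

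The SAP, Statistical analysis, does not define the variable further. It sets the scale: "As PAC burden is highly skewed, we pre-specified using log PAC burden for analysis and reported the ratio of geometric means". The regression there models the change in outcome by arm, adjusted for age stratum and the baseline value. The sample size is set on the same change in log PACs.

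**The concern.** The first term of the sum is plainly in beats. The other two are totals of couplets and triplets, which most naturally read as numbers of episodes. Adding them unweighted would then mix units, and the result would be ectopic events of up to three beats per hour under the name of PACs per hour. Beats in runs of four or more appear in no term.

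Two things would be at stake. Preliminary PAC data are a stated product of this pilot, so an understated level could be carried into later work. And if magnesium changed how ectopic beats cluster, a count of events and a count of beats would give different treatment ratios.

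**Working it through.** **Inputs.** From the documents: the three-term sum and the division by hours (Protocol, Measurements); the log scale and ratio of geometric means, and "0.79 standard deviation units with 80% power and 5% type I error (2-sided), assuming 5 participants would not complete follow-up" (SAP, Statistical analysis); 1:1 allocation (Protocol, Study participants). The documents give no ectopy shares and no SD for the change in log PACs, so all shares, counts and SDs below are assumptions.

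**The plan's own figure.** A two-sample t-test with d = 0.79, two-sided 5% and 80% power needs 26.15, so 27 per arm: 2 × 27 + 5 = 59, against the stated 60. It reproduces to within one participant. The effect is in SD units, so the count definition does not enter it.

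**Level, if the totals are episodes.** With I isolated beats, C couplets and T triplets, the sum divided by the beat count is k = (I + C + T)/(I + 2C + 3T). Per 100 events:

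- C/T = 5/1: k = 100/107 = 0.93
- C/T = 10/3: k = 100/116 = 0.86
- C/T = 15/5: k = 100/125 = 0.80

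**Level, if the totals are beats.** The sum is right for these terms, and weights of 2 and 3 would be the mistake: 94 + 10 + 3 = 107 (7% too many) up to 80 + 30 + 15 = 125 (25% too many).

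**Treatment ratio.** A participant's change in log burden on the event scale equals the change on the beat scale plus log(k at follow-up) − log(k at baseline). If the mix is stable, the added term is zero. For example, if every component halves, the ratio is 0.50 on either count. If treatment has no effect on rhythm at all, it does not alter k either, so the null comparison is valid whichever count is used. A k that differs between participants shifts the baseline covariate, but randomization gives no reason to expect bias from that.

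Distortion therefore needs a shift in mix caused by treatment. The table takes placebo as stable and expresses the log distortion in SD units for an assumed SD of 0.5 and of 1.5. The first four rows are the event ratio over the beat ratio; the last is three-term beats over all beats.

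| Assumed shift, active arm only | Distortion | Log | SD 0.5 | SD 1.5 |
|---|---|---|---|---|
| C/T from 10/3 to 5/1 | 0.935/0.862 = 1.08 | 0.081 | 0.16 | 0.05 |
| C/T from 15/5 to 5/1 | 0.935/0.800 = 1.17 | 0.155 | 0.31 | 0.10 |
| I/C/T 1000/100/30, C and T halve | (1065/1130)/(1145/1290) = 1.06 | 0.060 | 0.12 | 0.04 |
| I/C/T 1000/300/100, C and T halve | (1200/1400)/(1450/1900) = 1.12 | 0.116 | 0.23 | 0.08 |
| Longer runs from 5% to 10% of beats | 0.90/0.95 = 0.95 | −0.054 | 0.11 | 0.04 |

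(The last row shows absolute SD units.) With 27 and 28 completers, the unadjusted standard error of the difference is √(1/27 + 1/28) = 0.27 SD. The largest entry, 0.31, is 0.31/0.27 = 1.15 standard errors and 0.31/0.79 = 0.39 of the difference the trial was sized for. It needs the smallest assumed SD and the largest shift. The other entries are all below one standard error.

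**What the largest case requires.** A beat-based ratio of 0.90 would be reported as 0.90 × 1.168 = 1.05. Start from 80 isolated beats, 15 couplets and 5 triplets (125 beats). At follow-up there are 0.90 × 125 = 112.5 beats in a 94/5/1 mix, which is 112.5/1.07 = 105.1 events: 98.8 isolated, 5.3 couplets and 1.1 triplets. Isolated ectopy would have to rise about 24% while couplets fall about 65% and triplets about 79%. The 10/3 to 5/1 case, with total beats unchanged at 116, gives 116/1.07 = 108.4 events: isolated beats up about 17%, couplets down about 46%, triplets down about 64%.

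**The case for a change.** The best case for acting is that this is the only definition of the variable on which the trial was sized, and a reader cannot reproduce its level or compare it with another study without the unit. A definition in the source cited for the algorithm would not show how this trial combined the fields. The remedy looks cheap: one look at the export definition and, if needed, one re-derived variable. Nor does distortion need the implausible pattern of isolated beats rising; the halving rows in the table produce some with isolated beats constant.

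The part about the unit stands: it is not stated. The rest does not lead to a different plan. The documents do not show that the totals are episodes, and if they are beats, the proposed weights would introduce an error. Longer runs are not left open, because the definition is a closed list that does not contain them. Including them could add skew to an outcome the SAP already log-transforms for that reason. In the halving scenarios, events per hour and beats per hour answer slightly different questions about burden; the first is not a biased version of the second. Finally, the SAP is written in the past tense and already reports a post hoc analysis, so replacing the main count at this stage would itself be a post hoc change of outcome.

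**Conclusion.** No change to the plan is called for. The missing unit is a matter of labelling that an analyst settles by looking at the device export and stating it when the level is reported. Leaving out longer runs, and counting events if that is what was done, are choices on which reasonable statisticians differ.

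On the episode reading, the descriptive level is 0.80 to 0.93 of the three-term beat count, under couplet/triplet shares of 15%/5% to 5%/1% of events. On the beat reading there is no understatement of those three terms. The treatment ratio is unaffected if each participant's mix is stable, and the test of no effect is sound on either reading. A different ratio arises only if treatment changes clustering or the share of longer runs, which the documents neither show nor exclude. In the scenarios tried, that amounts to 0.04 to 0.31 SD, with the upper end resting on a strained shift and a small assumed SD. The sample size of 60 stands.
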